2.1 Trial Objectives

2.1.1 Primary Objective:

To determine if the routine use of IOCS during CS, in women at risk of haemorrhage, reduces the need for donor blood transfusion in comparison to current practice.

2.1.2 Secondary Objectives:

- To determine the effect of IOCS on secondary outcomes including the number of units of donor blood transfused, mean fall in serum haemoglobin level and maternal morbidity resulting from post-operative anaemia (time to first mobilisation, duration of hospital stay, and immediate post natal multidimensional fatigue inventory).
- To determine if the routine use of IOCS during CS, in women at risk of haemorrhage, is cost effective in comparison to current practice.

2.2 Trial Design

A multicentre individual randomised controlled trial with cost-effectiveness analysis.

2.3 Setting

[figure not shown]
At least seventeen large obstetric units supported by the Pragmatic Clinical Trials Unit (PCTU). The following table (Table 2) gives demographic details for proposed units (29):

Table 2: Proposed Trial Hospital Sites Annual C-sections and Deliveries

Hospital	CLRN	Proposed PI	Annual Deliveries	Annual C-Sections
Royal London Hospital	CEL	[name]	4400	1012
Homerton University Hospital	CEL	[name]	5000	1300
Queen's Hospital, Romford	CEL	[name]	8000	1840
Whipps Cross University Hospital	CEL	[name]	5500	1375
Guys & St Thomas' Hospitals NHS Trust	London (South)	[name]	7000	1890
John Radcliffe Hospital Oxford	Thames Valley	[name]	7000	1600
Birmingham Women's NHS Foundation Trust	BBC	[name]	7300	1825
Heart of England Hospital Foundation Trust	BBC	[name]	7000	1610
University Hospitals Coventry & Warwick	West Midlands (South)	[name]	6000	1560
Central Manchester University Hospital	Greater Manchester	[name]	6400	1216
Royal Hallamshire Hospital, Sheffield	South Yorkshire	[name]	7500	1725
St James University Hospital Leeds	West Yorkshire	[name]	5000	1150
Nottingham City Hospital	Trent	[name]	5793	1092
Newcastle Hospitals NHS Trust	Northumb, Tyne & Wear	[name]	7000	1750
Singleton Hospital Swansea	CRC Cymru	[name]	3800	874
Simpson Centre for Reproductive Health, Edinburgh	CRC Scotland	[name]	7000	1890
Hull and East Yorkshire NHS Trusts	North East Yorkshire and North Lincolnshire CLRN	[name]	5661	1313
Chelsea and Westminster Hospital	London NW CLRN	[name]	5646	2023
North Bristol NHS Trust	The Western CLRN	[name]	6435	1541
Total per year			117, 435	28, 586

3 Subject Selection

3.1 Figure 3: Anticipated Study Consort Diagram

3.2 Eligibility Criteria

Women who are admitted to a participating labour ward who fulfil all the following criteria will be eligible to be randomised.

3.2.1 Inclusion Criteria

- 16 years of age or older
- Delivery by elective or emergency caesarean section with an identifiable increased risk of haemorrhage.
- Ability to provide informed consent

3.2.2 Exclusion Criteria

- Elective first Caesarean section for maternal request or breech presentation; with no additional prognostic factor for haemorrhage
- Sickle cell disease
- Active malignancy contraindicated to CS e.g. abdominal cancer
- Cultural or social beliefs contraindicating blood transfusion e.g. Jehovah's Witnesses.
- Significant antibodies making it difficult to find cross matched blood for transfusion
- Unable to understand written and spoken English

The exclusion criteria above have been chosen for the following reasons;

- a. Elective first CS due to maternal request or breech presentation does not tend to put the mother at an increased risk of haemorrhage. All other indications for CS would be considered an identifiable increased risk of haemorrhage.
- b. Significant antibodies make it difficult to find cross matched blood because allogeneic blood for this group of patients is likely to be scarce or unavailable. We consider it appropriate to give these patients IOCS from the start of their case.
- c. Since donor red blood cell transfusion is the primary study outcome, individuals with cultural or social beliefs that preclude donor blood transfusion will be excluded from the study.
- d. Women with sickle cell disease have low levels of oxygen, this can cause the red blood cells to deform and block the microscopic blood vessels in the body. There is a chance that this "sickling" may occur while the blood is in the IOCS collection reservoir awaiting processing.
- e. Women with active cancer contraindicated to CS, especially cancer in the abdominal region, will be excluded as there is a theoretical risk of spreading the cancer should IOCS be used.

3.3 Protocol violations

A participant will be considered a protocol violator if, after randomisation:

e.g.

- They no longer meet eligibility criteria
- Due to safety concerns for the participant, or at investigator discretion, the opposite intervention (i.e. IOCS in the case of randomisation to routine practice) is definitely indicated
- Participant loses capacity to consent
- Participant withdraws their consent, to either allocated treatment and/ or to data collection.
- Participant no longer requires a caesarean section

3.4 Data Collection and Follow up for Withdrawing Participants

A participant can be withdrawn from the trial treatment if, in the opinion of the investigator or the care providing clinician or clinical team, it is medically necessary to do so. Withdrawal from follow-up is the decision of the participant. However, withdrawn participants can bias clinical trial results

and reduce the power of the trial to detect important differences. With any protocol violation, the study personnel will make every effort to obtain, and record, information about the reasons for violation, any adverse events and to follow-up the women for all safety and efficacy outcomes, as appropriate. If a woman decides after randomisation she does not wish to participate any further in the SALVO trial, she may withdraw herself from the trial. We will aim to document the reason for self-withdrawal. Clear distinction will be made as to whether the participant is withdrawing from trial whilst allowing further follow-up, or whether the participant refuses any follow-up. If a participant explicitly withdraws consent to have any further data recorded their decision will be respected and recorded on the final study form. All communication surrounding the withdrawal will be noted in the study records and no further data will be collected for that participant. They will be returned to the NHS standard practice for follow up care.

If a woman loses the capacity to consent during participation in the trial, they will be withdrawn from the trial and no further data will be collected from the participant unless consent for this was explicitly obtained prior to the loss of capacity.

Participants who are protocol violators will not be replaced by another participant as this has been accounted for in the sample size calculation and estimated at 1.2%.

3.5 Choice of outcome measure

The primary outcome will be use of donor blood transfusion. Reducing the proportion of women with this outcome should lead to fewer transfusion related complications. The treatment arms will be compared according to this outcome on an intention-to-treat basis. However, because clinicians managing women in the control arm will have access to an IOCS machine, it is possible that women in the control arm could receive IOCS in place of a donor blood transfusion. As a sensitivity analysis, we will analyse the primary outcome assuming that all instances of the use of IOCS in the control arm would have been instances of donor blood transfusion had the IOCS machine not been present. We will aim to minimise the sensitivity of the estimate of treatment effect to this assumption by promoting equipoise among participating clinicians and emphasising the importance of adherence to the protocol.

For the avoidance of doubt it is important to clarify terminology. Sometimes use of an intervention in the control group for whom it is not intended is described as ‘crossover’. This can be confusing as crossover trial is a specific trial design that we are not employing in our project. We have therefore refrained from the use of the term ‘crossover’ throughout this protocol.

4 Study Procedures

4.1 Informed Consent Procedures

As many women as possible booked to deliver at participating centres, whether they are intending a natural (vaginal) delivery or a caesarean section, will receive information about the study during their pregnancy and again on admission to delivery suite. This process will be individualised for each participating centre depending on their routine practice to ensure that the maximum number of women are offered information well in advance of delivery. For example, in some centres, women will be provided with information about the trial at their routine anomaly scan appointment (18-22 weeks). The provision of study information will be documented in the woman’s medical record or handheld notes, and a sticker applied to indicate whether they are or are not interested in taking part in the study, or whether they have not yet made up their mind. Also it will be further documented at this point if in an emergency situation they would still be interested in taking part in the study.

Written informed consent will be obtained by a health professional (obstetrician, anaesthetist or midwife) with delegated authority from the Principal Investigator. All women will be assessed to ensure that they have the capacity to provide consent. Consent will comprise a dated signature from the woman and the dated signature of the person who obtained informed consent. A copy of the signed informed consent document will be given to the woman. A copy will be retained in the woman's medical notes, a copy retained by the Principal Investigator in the investigator site file (ISF). The process and timing for obtaining written consent will vary according to clinical urgency (see below)

An investigator will be available at all times to discuss concerns raised by women or clinicians during the course of the trial. Information about the trial will continue to be offered to women after they leave the hospital. A regular newsletter will be produced giving women, and their families, up to date information about the trial until it has finished.

4.1.1 Elective Caesarean Section

Eligible women requiring elective CS will be provided with further information and the opportunity to ask questions at the time the operation is booked and approached for written consent at pre-operative assessment clinic or on the day of surgery. It will be clearly stated that she is free to withdraw from the trial at any time, for any reason, without prejudice to future care and with no obligation to give the reason for withdrawal. Randomisation will take place on the day of surgery.

4.1.2 Emergency Caesarean Section

A substantial challenge to the conduct of an individual RCT of IOCS is obtaining consent from women in labour who require emergency CS. This population may be the very individuals who derive specific benefit from this health technology and therefore their participation is vital.

As detailed above, as many women as possible booked for delivery at participating centres will have received the information regarding the trial during their pregnancy so that sufficient time is given to consider participation in the trial should an emergency caesarean section be required. On admission to delivery suite, women's notes will be checked to ensure this information was supplied, and the opportunity for further discussion provided. Eligible women interested in taking part will have this indicated on their medical notes if this has not been done previously.

Despite best attempts to ensure the maximum number of women receive information during their pregnancy, some women may arrive on delivery suite who have not previously received trial information. As discussed in Section 1.3.7, many of these women perceive cell salvage as reassuring and potentially beneficial and will wish to enter the trial to have the opportunity of receiving it in the event that they require a caesarean section. If they are not distressed, these women may have prolonged periods during which they are capable of reading and considering the SALVO information sheet, and subsequently giving informed consent for recruitment; this includes women in early labour, or who have effective epidural analgesia in progress.

Approaching Women In Early Labour

In routine practice, women who attend the delivery suite for assessment and are found to be in the latent first stage of labour (early labour) are offered individualised support and occasionally analgesia, and encouraged to return home as per NICE guidelines (NICE CG55 intrapartum care, 2007) or sometimes they remain in the hospital. Under either of these circumstances, a woman who meets the following criteria (ie she is not in established labour) may be offered trial information by the midwife caring for her:

- Woman is willing to receive the trial information and is subsequently willing to discuss the PIS and have any questions answered if desired.

- 0-3cm dilation, not contracting regularly (ie a maximum of one contraction in ten minutes, with contraction lasting less than 30 seconds).
- She will be advised that the person taking informed consent will return after 1 hour to see if she would be interested in taking part, should she require a caesarean section. If her situation changes and labour becomes established during that hour, or if she requires a caesarean section before the hour has elapsed, she will not be approached for inclusion. (If the woman has a contraction during the discussion about the study, the clinician involved will pause and wait for the contraction to finish. Permission to continue with the discussion will then be sought.)
- After the discussion, it will be recorded whether the woman is or is not willing to take part in the trial, should a caesarean section be required.
- **Women in established labour (ie 4cm and regular painful contractions) will not be approached for the first time on delivery suite.**
- **Women who are distressed and not in a position to absorb the information on the patient leaflet will not be approached for the first time on delivery suite.**

Approaching women with epidural

If a woman in labour has effective epidural analgesia in progress and is comfortable, she may be offered trial information by the midwife caring for her if the following criteria are met:

[figure not shown]
- Woman is willing to receive the trial information and is subsequently willing to discuss the PIS and have any questions answered if desired.
- She will be advised that the person taking informed consent will return after 1 hour to see if she would be interested in taking part, should she require a caesarean section. If her situation changes and she has not remained comfortable for that hour, or if she requires a caesarean section before the hour has elapsed, she will not be approached for inclusion.
- After the discussion, it will be recorded whether the woman is or is not willing to take part in the trial, should a caesarean section be required.

Consent will be obtained if a decision for caesarean section is made (see below). It will be clearly stated that she is free to withdraw from the trial at any time, for any reason, without prejudice to future care and with no obligation to give the reason for withdrawal.

The majority of emergency CSs in the absence of acute fetal distress are conducted in a controlled manner with ample time for regional anaesthesia to be established. In this context, it is feasible for written consent to be obtained at this stage once the decision for CS has been made.

However, in some emergency situations, the urgency of the situation means that for some women, it may not be possible to obtain written consent for the trial prior to the emergency CS. In this instance, where there is insufficient time for written consent to be obtained but the woman has capacity to consent and has previously indicated an interest in taking part in the trial, verbal consent will be obtained. Written consent will then be completed once the urgency of the situation is over and the caesarean section complete.

Figure 5: Procedures Flow Chart

4.2 Screening Procedures

To confirm eligibility for randomisation, investigators will need to verify women meet the inclusion/exclusion criteria for the trial as well as gaining informed consent. An eligibility checklist will be completed on the Randomisation Form, prior to randomisation. Participants who provide informed consent and are eligible for randomisation will have key parameters such as gestational age, indication for caesarean section, obstetric history, demographics and prognostic factors collected.

4.3 Randomisation Procedures

Once eligibility has been confirmed and consent has been obtained, the participant can be randomised to either caesarean section with IOCS or caesarean section with standard care. Randomisation will occur on the delivery ward, at the time women are being prepared for theatre.

Randomisation to the allocated intervention (allocation ratio 1:1) will use a bespoke web-based randomisation system hosted by Bristol Randomised Trial Collaboration (BRTC), University of Bristol as detailed in the relevant trial standard operating procedure (SOP). The randomisation will use random permuted blocks of variable sizes to ensure that trial staff conducting randomisation cannot reliably predict the next allocation.

Randomisation will be stratified, by four criteria:

1. Centre
2. Type of Caesarean (Emergency/Elective)
3. Presence of abnormal placentation
4. Multiple births (twins or more)

The procedures for randomisation will be fully documented, tested and validated prior to the start of the trial and monitored by the BRTC during the trial. Once the participant has been successfully randomised to the study, they will be added to the enrolment log.

Each participating centre will have access to the randomisation system with a unique hospital pin number. This will be restricted to staff as delegated by the Principal Investigator. They will input the details required for randomisation and immediate on-screen randomisation will occur. An email will be automatically generated to notify the chief investigator when each participant is randomised to the trial. This will be a blinded email devoid of any allocation information.

4.4 Methods for minimising the risk of bias

Allocation concealment with third party randomisation will help minimise *selection bias*.

Performance bias may lead transfusion rates to vary. We will minimise this risk by ensuring that each centre has an intra-operative transfusion protocol for use in theatre and recovery to standardise operative transfusion triggers across both study groups in each centre. A similar standardised checklist will be used to guide decisions on post-operative transfusion (See appendix 3 for example). Some centres may adopt an agreed haemoglobin threshold for transfusion, which should be applied equally to both groups. There is evidence that the presence of symptoms such as lassitude, dyspnoea and fatigue provide excellent surrogates to haemoglobin estimation to guide donor blood use (24). Maternal activity in the period immediately after CS and the demands of the tasks associated with care of the new-born are unlike most other contexts of recovery from an operative intervention where greater inactivity is considered the norm. To be pragmatic, the protocol may be allowed to vary between centres according to consensus opinion amongst clinicians. This represents real world variation in local practices and will not contribute to bias.

An attempt will be made to blind post natal carers to group allocation after CS. The allocation will not be recorded in routine case notes but this does not represent formal blinding as theatre notes will be available. The carers on post natal wards are a different group of staff to the carers on labour wards and operating theatres. It is on the post natal wards where the decisions for post-operative donor blood transfusions are made. This is based on the post-operative haemoglobin level and maternal symptoms. In the event of the need for a donor blood transfusion, serum haemoglobin (Hb) will be measured by blood sample, pre and post-transfusion and results recorded. This will allow monitoring of numeric transfusion thresholds between units and groups. In the unlikely event that between group variations in haemoglobin transfusion triggers were indeed evident, consideration would be given for adjusting for such differences in the final analysis. It is worthy of note that alternative trial designs, such as cluster randomisation, would not necessarily minimise the performance bias problem (section 2.2 on choice of design); it would simply reduce the power.

4.5 Preparing and supporting theatre and medical staff for participation in the trial

The use of the IOCS machine represents an additional task for theatre personnel and medical staff to undertake during a caesarean section, which is of particular importance in an emergency situation. It will therefore be crucial to the success of the trial that all staff are sufficiently trained and familiar in the use of the IOCS machine. IOCS technology is already present at participating centres with many theatre staff skilled in its use. Training will be conducted by manufacturers of the IOCS machine and the trial coordinating centre prior to recruitment of participants, at site initiation and training visits.

4.6 Schedule of Treatment

Women will be randomly allocated to either:

1. Caesarean section with IOCS (intervention group), set up routinely with collection of shed blood from the outset of surgery, and return of any processed blood obtained.
2. Caesarean section without IOCS (control group), with transfusion of donor blood according to standard local guidelines.

Blood will be aspirated from the surgical field; the red cell component isolated by centrifugation and after washing and filtration, re-transfused. The ability to return salvaged blood is dependent on sufficient volume being collected and processed. Blood will be uniformly returned to women in the IOCS group if this volume threshold is reached. The control group will receive standard current practice (without IOCS), which may involve donor blood transfusion. In life threatening acute haemorrhage, women will be managed at the discretion of attending clinicians, in line with Centre for Maternal and Child Enquiries (CEMACE) guidance, potentially including the use of IOCS in the control arm. We anticipate this to be a very rare occurrence. The indications for postoperative donor blood transfusion will be set according to local protocols in each hospital and deviations from this criterion will be monitored.

4.7 Table 3: Schedule of Assessment

	Pre-operative	Intra- operative	Post-operative (24 hours)	Discharge
SCREENING				
Eligibility	X			
Informed consent	X			
Obstetric History/Prognostic Factors/ Indication CS/Demographics	X X			
Randomisation	X			
TRANSFUSION				
Transfusion of ≥ 1 unit donor blood		X	X	
Number of donor blood units transfused		X	X	
Volume of blood returned by IOCS		X		
IOCS consumables used		X		
IOCS technical failure		X		
MATERNAL				
Haemoglobin level	X		X	
Maternal exposure to fetal blood (Kleihauer test)			X	
Transfusion reaction			X	
Anti D requirement and dose			X	
Time to first mobilisation after CS			X	
Multidimensional Fatigue Inventory (MFI)				X
HEALTHCARE UTILISATION				
Length of hospital stay				X
Adverse Events		X	X	X

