1.3.9 Audit of transfusion rates in Caesarean Section

A detailed audit of donor blood use at the Royal Hallamshire Hospital Sheffield 2009-10, without IOCS in routine use, was performed by cross-reference of perioperative records, blood bank data and electronic records stored in cell salvage machines. It reported that in a recent series of 1647 CS over 10 months, 89 women were transfused with donor blood, giving a rate of 5.4% ([name], Personal communication). A similar audit at Birmingham Women's Hospital of all CS carried out in 2006, showed that of 1674 women, 83 (5.0%) received a transfusion, with a mean transfusion volume of 1620ml SD 1350ml (1). This equates to 3.6 +/- 3 units of donor blood administered. Both auditing units deliver approximately 7300 women per year with a similar CS rate and can be considered representative of UK tertiary obstetric unit practice.

It is important to note that these data include both acute transfusion at operation and any donor blood given in the postoperative period to treat symptomatic anaemia before hospital discharge. Our study population is defined by women undergoing CS who have at least one identifiable risk factor for haemorrhage. We have defined 'Increased risk of haemorrhage' to include elective CS for abnormal placentation and previous CS and all emergency CSs. The emergency CS group includes a number of indications which are at particularly high risk of haemorrhage including antepartum haemorrhage and pre-eclampsia. The baseline transfusion requirement of this selected population is likely to be elevated. For example, a recently published study of 246 Caesarean deliveries for placenta praevia reported 29% of cases required transfusion. Of those women who received donor blood, 63% required 3 units or more (23).

2 Trial Objectives and Design

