7.1 Trial Outcomes

7.1.1 Primary outcome

The primary outcome is the proportion of women needing donor blood transfusion to deal with haemorrhage and its consequences. (see section 3.5).

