The expected effect estimate can be derived from the literature. Our systematic review (1) and its most recent update has shown only one small trial published in 1998 (3), which randomised a total of 68 participants to either IOCS or standard care. The transfusion rate in the control group was 23.5% and 2.9% in the IOCS group. The control event rate is considerably higher than that observed in current UK practice and inconsistent with literature from other sources. It is likely to be due to a sample at exceptionally high risk of haemorrhage. Weaknesses that raise the risk of bias (e.g. inadequate concealment of randomisation) preclude reliance on it alone to inform our calculations. Non-obstetric literature evaluating IOCS in interventions with a moderate to high risk of transfusion has two high quality systematic reviews: a HTA report citing a RR of exposure to allogeneic blood of 0.59 (95% CI 0.48-0.73) with salvage (6); and a Cochrane review reporting a RR of 0.62 (95% CI 0.50-0.70) for transfusion with salvage compared with normal practice (7). Detecting smaller effect size is possible but the larger sample size required has to be balanced against the cost and practicability of undertaking such a trial. From the current best literature we assume an intervention effect at or around 0.6 (at a control event rate of 5%, the intervention group would have a transfusion rate of 3%).

We have discussed the issue of directionality of hypothesis and significance testing and provided a range of sample sizes in table 6. Figure 6 shows how the power of our 3050 sample changes across a range of control event rates (between 4-7%), experimental event rates (between 2-4%) and directionality of hypothesis (1- or 2-sided test).

Control event rate	Two sided test Power 80%	Two sided test Power 90%	One sided test Power 80%	One sided test Power 90%
7%	2116	2830	1666	2308
6%	2490	3332	1960	2714
5%	3012	4032	2374	3286
3%	5106	6836	4022	5570

The interim analysis of our pilot study has confirmed that primary outcome data can be obtained in virtually all the randomised women, since this information is collected at the end of the in-patient stay before hospital discharge. Our sample size allows for primary outcome data and follow up loss of around 1% (38) randomised cases.

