8.3 Case Report Forms

For all participating women, pre-operative trial data will be recorded in the maternity notes which will be completed by the attending obstetrician, anaesthetist or midwife. The following data will be abstracted from the notes and recorded on CRF for the trial, relying on CLRN research support in each of the recruiting hospitals.

Pre-Operative

- Demographic data
- Obstetric history
- Gestational Age/Prognostic factors/Indication for CS
- Pre-op Hb level

Intra/Post-Operative

- AE/SAE Log

Further information will be collected during intra-operative and post-operative phase and at the time of discharge from hospital. This data will be recorded directly to trial CRF's by the attending obstetrician, anaesthetist or midwife as outlined on the trial delegation log. Any missing information will be obtained from trial participant prior to discharge. Checking of this data, along with administration of multidimensional fatigue inventory on the post natal wards, will rely on CLRN research support in each of the recruiting hospitals. No further routine follow up will be required after discharge.

The following trial specific data which will be entered directly to CRF:

Pre-Operative

- Eligibility criteria checklist

Intra-Operative

- Transfusion of ≥ 1 unit donor blood
- Number of donor blood units transfused
- Volume of blood returned by IOCS
- IOCS consumables used
- IOCS technical failure
- Maternal exposure to fetal blood

Post-Operative

- Transfusion of ≥ 1 unit donor blood
- Number of donor blood units transfused
- Hb level
- Transfusion reaction
- Anti D requirement and dose
- Time to first mobilisation after CS

Discharge

- Multidimensional Fatigue Inventory (MFI)
- Length of stay in Hospital

Other

- Additional Information/Note to File CRF
- Final Study Status /Early Withdrawal CRF

Suitably qualified members of the study team, as documented on the trial delegation log will be responsible for the completion of the CRFs. CRFs will be pseudonymised using a participant code allocated at time of randomisation. The number will be generated by the online randomisation system and recorded on the Randomisation Form. This code will consist of the trial site code followed by the consecutive recruitment number starting at 001. Site codes are documented in Appendix 4.

E.g.: Royal London Hospital (01), participant number 1 (001) : 01001

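### Table 3 schedules the primary outcome only to 24 hours after surgery, which contradicts the to-discharge collection in section 7.5 and the audits behind the 5% planning rate

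*Protocol*

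**What the plan says.** **Schedule.** In Table 3 (Protocol 4.7) the row "Transfusion of ≥ 1 unit donor blood" and the row for number of donor units are ticked under Intra-operative and under the column that begins "Post-operative (24 hours". Discharge is blank for both. The Adverse Events row of the same table is ticked in all three of these columns.

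**Sample size.** Section 7.5 expects almost complete primary outcome data "since this information is collected at the end of the in-patient stay before hospital discharge".

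**Planning rate.** The 5% control rate rests on published observational reports and on audits in two centres. Section 1.3.9 says the audit counts include acute transfusion at operation and "any donor blood given in the postoperative period to treat symptomatic anaemia before hospital discharge".

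**Definition.** Section 7.1.1 reads "The primary outcome is the proportion of women needing donor blood transfusion to deal with haemorrhage and its consequences" and refers the reader to section 3.5, which says "The primary outcome will be use of donor blood transfusion". Neither gives a start or an end.

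**Case report form.** Section 8.3 lists transfusion and units under Intra-Operative and again under Post-Operative, with no hour limit on the latter. Its Discharge block holds only the fatigue inventory and length of stay. Its general sentence is "Further information will be collected during intra-operative and post-operative phase and at the time of discharge from hospital".

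**Where transfusion is decided.** Section 4.4 places post-operative transfusion decisions on the postnatal wards, based on haemoglobin and symptoms.

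**The concern.** The period over which events count is part of the definition of a binary primary outcome. Here one part of the protocol points to 24 hours and another to discharge, and the definition itself does not decide between them. The schedule of assessment is the page that sites work from, so its ticks matter in practice.

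The events in doubt are relevant ones. Transfusion for symptomatic anaemia is decided on the ward and can fall after the first day, and sections 1.1 and 1.3.2 name less post-operative anaemia as a possible benefit of cell salvage. A literal 24-hour capture could remove part of the effect under study and lower the event rate. If some centres stop at 24 hours and others record to discharge, the outcome would not mean the same thing everywhere. The same records also feed the volume of blood transfused (7.1.2), donor units as a resource (7.7.1) and cost per transfusion avoided (7.7.2). A later analysis plan can define a window, but it cannot restore data that no form asked for.

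**Working it through.** **1. The passages side by side**

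| Place in Protocol | Window for donor transfusion |
|---|---|
| Table 3 (4.7) | Surgery and 24 hours post-operatively; Discharge blank |
| 7.5 | Collected at end of in-patient stay |
| 1.3.9 (audits) | Operation to discharge |
| 7.1.1 and 3.5 | None stated |
| 8.3 | Intra-operative and post-operative, no hour limit; not in Discharge block |

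The blank Discharge cell is unlikely to be a general habit of the table. Adverse Events is ticked there, in line with section 7.4, which records adverse events from randomisation to discharge.

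The Post-Operative block in 8.3 does not break the tie. Its items (transfusion, units, haemoglobin, transfusion reaction, anti-D, time to mobilisation) are those of Table 3's 24-hour column, except the Kleihauer test, since 8.3 lists maternal exposure to fetal blood as intra-operative. A site could reasonably treat block and column as the same visit. The promise in 8.3 to obtain missing information before discharge does not help either, because a form completed at 24 hours has nothing missing.

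**2. The plan's own figure**

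Inputs from 7.2, 7.5 and 4.3: control 5%, intervention 3%, two-sided alpha 5%, power 80%, allocation 1:1.

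n per arm = [1.960·√(2·p̄·(1−p̄)) + 0.842·√(p1(1−p1) + p2(1−p2))]² / (p1−p2)², with p̄ = 0.04.

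- √(2 × 0.04 × 0.96) = 0.2771
- √(0.0475 + 0.0291) = 0.2768
- (1.960 × 0.2771 + 0.842 × 0.2768)² / 0.02² ≈ 1,506 per arm
- Total 3,012, as in the table of section 7.5. Adding the 38 allowed for loss gives 3,050.

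Power with all 1,525 per arm is 80.5%. The arithmetic of the plan is sound.

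**3. Illustration of a literal 24-hour window**

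The share m of transfusions given after 24 hours is not in the documents, so it is assumed. Both arm rates are multiplied by (1 − m), and the relative risk stays at 0.6. Power = Φ{[(p1−p2)·√n − 1.960·√(2·p̄·(1−p̄))] / √(p1(1−p1) + p2(1−p2))} with n = 1,506 per arm.

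| Assumed m | Control vs cell salvage | Power | Total evaluable for 80% power |
|---|---|---|---|
| 0% | 5.0% vs 3.0% | 80% | 3,012 |
| 10% | 4.5% vs 2.7% | 76% | 3,362 |
| 20% | 4.0% vs 2.4% | 70% | 3,798 |
| 40% | 3.0% vs 1.8% | 58% | 5,106 |

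Worked line for m = 20%: (0.016 × 38.81 − 1.960 × 0.2489) / 0.2486 = 0.535, and Φ(0.535) = 0.70. The last total, 5,106, is also the protocol's own entry for a 3% control rate.

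**The case against.** The strongest reply is that the protocol as a whole points to discharge and that Table 3 merely has a loose column label. Section 7.5 says outright that "this information is collected at the end of the in-patient stay before hospital discharge". Section 7.7 describes follow-up as lasting until discharge. Section 4.4 records haemoglobin around donor transfusion with no time limit. Section 8.3 sets no 24-hour limit and has research staff checking data on the postnatal wards. The 24-hour column also holds time to first mobilisation, which section 7.6 analyses as a time-to-event outcome, so a hard cut-off was perhaps not meant.

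Much of this stands. A reader might infer that the case report form itself stops at 24 hours, or that later transfusions will certainly be lost. The documents support neither. The form list only lacks a discharge item, and loss occurs only where a site takes Table 3 at its word.

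The power figures can also be challenged. The late share is assumed. The relative risk is held at 0.6, although it would change if cell salvage acts differently on early and late transfusions. Section 1.3.9 expects the selected population to need more transfusion than the audited one, so a rate below 5% is not established.

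A reader might also infer that the word needing in 7.1.1 lets unblinded staff choose which transfusions count. That is weak: 7.1.1 refers to 3.5, where the outcome is use, and 8.3 records any transfusion of at least one unit and lists no field for cause.

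What the reply does not remove is the contradiction between Table 3 and section 7.5, with no stated window to settle it.

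**Conclusion.** The point holds as an unreconciled window for the primary outcome. Table 3 stops at 24 hours, section 7.5 and the audits run to discharge, section 7.1.1 is silent, and section 8.3 does not decide. The likely intention is discharge, but a site following the schedule literally could miss later ward transfusions, and centres could differ.

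The size cannot be fixed from the documents. The fall to 76%, 70% or 58% power is an illustration that rests on an assumed late share of 10%, 20% or 40%, a constant relative risk of 0.6, a 5% to-discharge control rate and literal use of Table 3 at every site. It is not evidence that the trial is underpowered: with capture to discharge, 3,050 women give the power that the protocol states. The correction is still worth making in the protocol, because it concerns data collection for the primary outcome.

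**What to change.** - In 7.1.1, and consistently in 3.5 and 7.6, define the primary outcome once: receipt of at least 1 unit of donor blood from randomisation to hospital discharge.
- In Table 3, tick both transfusion rows under Discharge.
- In the Discharge block of 8.3, add one item: any further donor units since the post-operative form, with number and date.

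The sample size stays at 3,050, and neither treatment nor visits change. The cost is one sentence, two ticks and one extra form item, filled from existing hospital records.
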